7.3.2 Safety

Safety assessments will consist of monitoring and recording all adverse events, including serious adverse events, the monitoring of hematology, blood chemistry, ECG and the regular monitoring of vital signs, and physical exam including weight and performance status.

These assessments should be performed within ± 8 days of the scheduled day of assessment except for adverse events that will be evaluated continuously through the study. Safety and tolerability will be assessed according to the NCI CTCAE v4.

BGJ398 (infigratinib) has been well tolerated in its phase I, expansion, and phase II studies to date.

Post-biopsy patients will be followed closely for any evidence of complications. Dose delay rules will be closely followed as outlined (Section 6.1.5). In addition the Treating Investigator may elect to further delay treatment if any serious concerns about wound healing or unexpected events should occur.

7.3.3 Pharmacokinetics

BGJ398 (infigratinib) will be dosed at the established phase II dose, 125 mg PO daily. No specific pharmacokinetics will be obtained.

7.3.4 Correlative Analysis

For Details on FGFR aberration testing please see Section 4.1.1

FGFR profiling will be performed in the following two scenarios:

1. Genomic profiling to identify FGFR altered tumors and correlation of specific genetic changes with efficacy.
2. Tumors that respond and subsequently developed resistance (acquired resistance) will be biopsied to explore mechanisms of resistance to FGFR inhibition. Analysis of such tumors may be broader and include exome sequencing, RNA-seq analysis or similar tests.

While requirements for tissue and correlational studies are clearly stated and are to be implemented stringently, medical necessity, e.g. in the case of potential harm to the patient, or other extenuating circumstances may trigger a review and possible waiver per the PI on rare occasions.

Archival Tissue and Blood:

In addition to FGFR testing all patients are required to provide ≥ 10 unstained FFPE slides. This requirement can be waived only if a fresh tumor biopsy provides adequate tissue or per discussion with the Lead Investigator ([name]).

All patients are required to collect blood for banking of normal DNA

→ See Appendix B for tissue collection form

7.3.5 Tumor Biopsies

1) If no archival tissue for FGFR genetic aberration testing is available a fresh tumor biopsy is encouraged, and should typically be processed as a fresh frozen biopsy with OCT embedding. Please contact the Lead Investigator ([name] at [contact] or [contact] for more details).

2) Tumors that showed benefit from therapy (= RECIST response, or prolonged disease stabilization ≥ 6 months) and subsequently progress are required to undergo a fresh biopsy.

Biopsy should be performed preferentially by a surgeon (excisional biopsy or core needle biopsy (3-4 cores) or via interventional radiology (core biopsy (3-4 cores))). A large (several pass) bronchoscopic biopsy is potentially also acceptable, but a discussion about the amount of required tissue between the Treating Investigator and the pulmonary attending performing the procedure is required prior to biopsy. An FNA is not acceptable.

Biopsy in the above two scenarios is mandatory.

Typically a biopsy should be done in a lesion that is not the **only lesion** for RECIST measurement. A waiver of this requirement can be obtained after discussion with the Lead Investigator ([name]; [contact] or [contact]).

7.3.6 Biopsy safety considerations

Biopsies (core biopsies and small excisional biopsies) are generally considered safe during administration of treatment. Nevertheless in difficult to assess/high risk locations the treatment may be held for 2 days prior to biopsy and 3-5 days afterwards. For larger scale surgeries or should bleeding or wound healing complications arise the treating investigator should contact the Lead Investigator in order to get approval to continue holding therapy and will assess how long to hold treatment on a cases by case basis.

8 Data Reporting

Data reporting will be performed utilizing the eVelos electronic data capture system. The University of Chicago CRA will provide applicable user registration information.

All required data must be recorded in the eVelos database at the completion of each cycle. AEs are to be entered in real time. SAEs are to be entered on the Serious Event Form within 24 hours of the site's knowledge of the event and sent via email (preferred) or fax to the University of Chicago ([contact] or [contact]; [contact]). All case report forms must be completed by designated study personnel. Each screened (consented) patient is to be entered into eVelos within 48 hours of patient registration. In addition to direct data entry, you may be required to provide supporting source documentation. Source records are original documents, data, and records (e.g., medical records, raw data collection forms, pharmacy dispensing records, recorded data from automated instruments, laboratory data) that are relevant to the clinical trial. Each site will prepare and maintain adequate and accurate source documents. These documents are designed to record all observations and other pertinent data for each subject enrolled in this clinical trial. Source records must be adequate to reconstruct all data transcribed onto the case report form.

9 Registration Procedures

9.1 General Guidelines

Prior to registration and any study-specific evaluations being performed, all patients must have given written informed consent for the study and must have completed the pre-treatment evaluations. Patients must meet all of the eligibility requirements listed in Section 5. Eligible patients will be entered on study centrally by the University of Chicago study coordinator. All sites should call the study coordinator at [contact] or [contact] to verify availability of a slot.

Following registration, patients (must/should) begin protocol treatment within 7-10 business days. Issues that would cause treatment delays should be discussed with the Lead Investigator. If a patient does not receive protocol therapy following registration, the patient's registration on the study will be canceled. The study coordinator/CRA should be notified of cancellations as soon as possible.

9.2 Registration Process

When a potential patient has been identified, notify the CRA via phone or email to ensure a reservation on the study ([contact] or [contact]). Reservations for potential subjects will only be held for subjects who have signed consent for that particular study.

When registering a subject, the following must occur:

- Confirm that the institution has a current IRB approval letter for the correct version of protocol/consent and has an annual update on file, if appropriate.
- Submit all required materials (Eligibility Checklist, Source documentation, & signed consent form) to confirm eligibility and required pre-study procedures to the CRA a minimum of 48 hours prior to the subject's scheduled therapy start date.
- Source documentation includes copies of all original documents that support each inclusion/exclusion criteria. The eligibility checklist does not serve as source documentation but rather as a checklist that original source documentation exists for each criterion.
- Communicate with the above CRA to ensure all necessary supporting source documents are received and the potential subject is eligible to start treatment on schedule. If there are questions about eligibility, the CRA will discuss it with the PI. PI may clarify, but not overturn, eligibility criteria.
- Affiliate sites must confirm registration of subjects by obtaining a subject study ID number from the CRA via phone, fax or email.
- If a subject does not start on the scheduled day 1 treatment date, promptly inform the CRA as the delay in start may deem the subject ineligible and/or require further or repeat testing to ensure eligibility.
- The date the patient is randomized if randomization is involved or receives treatment for the first time will be considered the patient's "OnStudy Date." The patient's subject ID will be assigned and a confirmation of registration will be issued by the CRA on this date. Subjects that sign consent and do not go "OnStudy" will be recorded in the database with the date they signed consent and the reason for not going "OnStudy" (e.g., Ineligible, Screen Failure or Withdrawn Consent).

10 Safety monitoring and reporting**10.1 Adverse Events****10.1.1 Definitions and reporting**

Adverse event (AE) monitoring and reporting is a routine part of every clinical trial. The following list of AEs expected by the investigational agent (Section 10.1.2) and the characteristics of an observed AE (Section 10.2) will determine whether the event requires expedited reporting **in addition** to routine reporting.

10.1.2 Adverse event list

Adverse reactions are listed below by MedDRA body system organ class.
The following convention has been utilized for the classification of frequency:

Very common ≥ 1 in 10

Common ≥ 1 in 100 and < 1 in 10

Uncommon ≥ 1 in 1,000 and < 1 in 100

Categories have been assigned based on absolute frequencies in the clinical trial data.

ADVERSE EVENT CATEGORY	VERY COMMON	COMMON	UNCOMMON	EXPEDITED REPORTING IF GRADE > 2
Blood and lymphatic system disorders			X	
Endocrine disorders			X	X
Metabolism and nutrition disorders			X	
Nervous system disorders			X	
Cardiac disorders			X	X
Vascular disorders			X	
Hemorrhages			X	
Gastrointestinal disorders			X	
Hepatobiliary disorders			X	
Skin and subcutaneous tissue disorders			X	
Renal and urinary disorders			X	

General disorders and administration site conditions			X	
Corneal/ophthalmic disorders			X	

10.2 Adverse Event Characteristics

- CTCAE term (AE description) and grade:** The descriptions and grading scales found in the revised NCI Common Terminology Criteria for Adverse Events (CTCAE) version 4.0 will be utilized for AE reporting. All appropriate treatment areas should have access to a copy of the CTCAE version 4.0. A copy of the CTCAE version 4.0 can be downloaded from the CTEP web site http://ctep.cancer.gov/protocolDevelopment/electronic_applications/ctc.htm.
- Special AE expedited reporting:**
 AEs in the table under section 10.1.2 should undergo expedited reporting if the grade is above the grade provided in column labeled “Expedited Reporting if Grade > 2”.
- Attribution of the AE:**
 - Definite (5) – The AE *is clearly related* to the study treatment.
 - Probable (4) – The AE *is likely related* to the study treatment.
 - Possible (3) – The AE *may be related* to the study treatment.
 - Unlikely (2) – The AE *is doubtfully related* to the study treatment.
 - Unrelated (1) – The AE *is clearly NOT related* to the study treatment.

10.3 Adverse Event Definitions

10.3.1 Adverse Event

An adverse event is any untoward medical occurrence in a patient or clinical investigation subject administered a pharmaceutical product that does not necessarily have a causal relationship with the treatment. An adverse event can be any unfavorable and unintended sign (including a laboratory finding), symptom or disease temporally associated with the use of a medicinal (investigational) product, whether or not related to the medicinal (investigational) product.

At each evaluation patients should be interviewed in a non-directed manner to elicit potential adverse reactions from the patient. The occurrence of an adverse event will be based on changes in the patient's physical examination, laboratory results, and/or signs and symptoms, and review of the patient's own record of adverse events.

Adverse events will be followed until resolution while the patient remains on-study. Once the patient is removed from study, events thought to be related to the study medication will be followed until resolution or stabilization of the adverse event, or until the patient starts a new treatment regimen, or death, whichever comes first.

10.3.2 Serious Adverse Event

An adverse event is considered serious if it results in **ANY** of the following outcomes:

- 1) Death
- 2) Life-threatening (e.g. places subject at immediate risk of death, this does not include events that might have caused death if they occurred a greater severity)
- 3) Results in inpatient hospitalization or prolongation of existing hospitalization for ≥ 24 hours
- 4) A persistent or significant incapacity or substantial disruption of the ability to conduct normal life functions
- 5) A congenital anomaly/birth defect.

Important Medical Events (IME) that may not result in death, be life threatening, or require hospitalization may be considered serious when, based upon medical judgment, they may jeopardize the patient or subject and may require medical or surgical intervention to prevent one of the outcomes listed in this definition.

10.3.3 Unexpected Events

Unexpected events are those not listed at the observed specificity or severity in the protocol, informed consent, or investigator brochure. An event is considered unexpected if it is listed as occurring within the class of drugs or otherwise expected from the drug's pharmacological properties but which has not been previously observed with this specific investigational agent.

10.3.4 Adverse Reactions

An adverse event is considered to be an adverse reaction if there evidence to suggest a causal relationship to the study agent. This may include a single occurrence of an event strongly associated with drug exposure (e.g. Stevens-Johnson Syndrome), one or more occurrence of an event otherwise uncommon in the study population, or an aggregate analysis of specific events occurring at greater than expected frequency.

10.4 Adverse Event Reporting Requirements

10.4.1 Routine adverse event reporting

All Adverse Events **must** be reported in routine study data submissions. **AEs reported using the Serious Event Reporting Form and/or MedWatch Form discussed below must also be reported in routine study data submissions.**

All adverse events (except grade 1 and 2 laboratory abnormalities that do not require an intervention), regardless of causal relationship, are to be recorded in the case report form and source documentation. The Site Investigator must determine the intensity of any adverse events according to the NCI Common Terminology Criteria for Adverse Events (CTCAE) Version 4.0 and their causal relationship.

10.4.2 Serious adverse event reporting to the Coordinating Center

Use the UC CCC protocol number and the protocol-specific patient ID assigned during trial registration on all reports.

All serious adverse events (as defined in sections 10.3.2) and all adverse events that have been specified to require expedited reporting in the section 10.1.2 table occurring on this study require expedited reporting to the University of Chicago Comprehensive Cancer Center (UC CCC) Clinical Trials Office (CCTO). The responsible Research Nurse or other designated individual at the treating site should report the SAE to the CCTO by the end of the business day when s/he becomes aware of the event. Events occurring after business hours should be reported to the CCTO by 12pm (noon) the next business day.

Reports should be made using the 'Serious Event Report' Form. Please scan and send via email (preferred) or fax to the following:

University of Chicago Phase II CRA General:

[contact]

[contact]

[contact]

UC CCC Cancer Clinical Trials Office Quality Assurance:

[contact]

All unexpected adverse reactions must be reported to the IND holder so that the University of Chicago CCTO can inform the FDA. The responsible Research Nurse or other designated individual at the treating site should provide a complete written report using the FDA MedWatch 3500A form. The completed form should be sent to the CCTO at [contact], within the specified timelines below regardless of whether all information regarding the event is available. If applicable, a follow-up report should be provided to the CCTO if additional information on the event becomes available.

Participating sites should not forward any adverse event reports directly to the FDA. The CCTO will report all events to the FDA as per the current FDA guidelines.

Fatal or Life-threatening Events: within 4 calendar days from treating investigator knowledge of the event

All Other Reportable Events: within 10 calendar days of treating investigator knowledge of the event

All serious adverse events should also be reported to the local IRB of record according to their policies and procedures.

10.4.3 Serious and Unexpected Adverse Event reporting by the Coordinating Center

The designated UC CCC Regulatory Manager will notify all participating sites of all unexpected and serious adverse reactions that occur on this clinical trial and which are reported to the FDA and/or UC Institutional Review Board (IRB). When reported to the FDA, a copy of the completed Form 3500A (MedWatch) will be provided to the responsible Regulatory Manager by the CCTO IND Coordinator for distribution to all participating sites.

10.4.4 Reporting Requirements for the Institutional Review Board

At the University of Chicago: Events meeting current IRB reporting criteria must be submitted by the principal investigator via the IRB's electronic submission system within **the IRB's designated reporting timeframes**. Details of the IRB's current reporting policy and timelines can be found on their website at: <http://bsd.uchicago.edu/forms-guidelines/up.html>

At other centers: the local regulations for reporting to the IRB overseeing clinical research should be followed by the individual sites.

10.4.5 Novartis instructions for rapid notification of serious adverse events

All serious adverse events must be reported to Novartis Pharmaceuticals Drug Safety and Epidemiology Department (DS&E) and reporting will be done via the coordinating center (Univ. of Chicago). . Applicable events will be reported to the IRB and FDA as per their current policies.

All events reported to the FDA by the investigator are to be filed utilizing the Form FDA 3500A (MedWatch Form).

All events must be reported, by [contact]) to Novartis Pharmaceuticals DS&E Department within 24 hours of learning of its occurrence. This includes serious, related, labeled (expected) and serious, related, unlabeled (unexpected) adverse experiences. All deaths during treatment or within 30 days following completion of active protocol therapy must be reported within 24 hours.

Any serious adverse event occurring after the patient has provided informed consent and until 4 weeks after the patient has stopped study participation must be reported. This includes the period in which the study protocol interferes with the standard medical treatment given to a patient (e.g. treatment withdrawal during washout period, change in treatment to a fixed dose of concomitant medication).

Serious adverse events occurring more than 4 weeks after study discontinuation need only be reported if a relationship to the Novartis study drug (or therapy) is suspected.

For Comparator Drugs/Secondary Suspects (Concomitant Medications), all serious adverse experiences will be forwarded to the product manufacturer by the investigator.

10.5 Pregnancies

Any pregnancy that occurs during study participation should be reported by the site. To ensure patient safety each pregnancy must also be reported to Novartis within 24 hours of learning of its occurrence. The pregnancy should be followed up to determine outcome, including spontaneous or voluntary termination, details of birth, and the presence or absence of any birth defects, congenital abnormalities or maternal and newborn complications.

Pregnancy should be recorded on a Clinical Study Pregnancy Form and reported by the investigator to the oncology Novartis Drug Safety and Epidemiology (DS&E) department. Pregnancy follow-up should be recorded on the same form and should include an assessment of the possible relationship to the Novartis study treatment of any pregnancy outcome. Any SAE experienced during pregnancy must be reported on the SAE Report Form.

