Investigational treatment	Drug whose properties are being testing in the study as well as their associated placebo and active treatment controls (when applicable). This also includes approved drugs used outside of their indication/approved dosage, or that are tested in a fixed combination. Investigational treatment generally does not include other study treatments administered as concomitant background therapy required or allowed by the protocol when used in within approved indication/dosage
Medication number	A unique identifier on the label of each study treatment package which is linked to one of the treatment groups of a study.
Other study treatment	Any drug administered to the patient as part of the required study procedures that was not included in the investigational treatment
Subject Number (Subject No.)	A unique identifying number assigned to each patient/healthy volunteer who enrolls in the study
Phase	A subdivision of the study timeline; divides stages into smaller functional segments such as screening, baseline, titration, washout, etc.
Premature patient withdrawal	Point/time when the patient exits from the study prior to the planned completion of all study treatment administration and/or assessments; at this time all study treatment administration is discontinued and no further assessments are planned, unless the patient will be followed for progression and/or survival
Randomization number	A unique treatment identification code assigned to each randomized patient, corresponding to a specific treatment arm assignment
Stage related to study timeline	A major subdivision of the study timeline; begins and ends with major study milestones such as enrollment, randomization, completion of treatment, etc.
Stage in cancer	The extent of a cancer in the body. Staging is usually based on the size of the tumor, whether lymph nodes contain cancer, and whether the cancer has spread from the original site to other parts of the body
Stop study participation	Point/time at which the patient came in for a final evaluation visit or when study treatment was discontinued whichever is later

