3.2 Secondary Objectives

	Objective	Endpoint/Analysis
Secondary	Assess safety and tolerability of BGJ398 (infigratinib) in patients with Head and Neck Cancer	AE / SAE
Secondary	Assess duration of response, progression free and overall survival	DOR / PFS* / OS**

*Progression-free survival [days] = date of progression (or of death if no earlier progression) – date of randomization +1

*Progression-free survival (censored) [days] = date of last adequate assessment per RECIST 1.1 with negative imaging before patient withdrawal of consent or start of new therapy – date of randomization +1

**Overall survival [days] = date of death – date of randomization +1

Trial termination is synonymous with off study / end of treatment.

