3.3 Exploratory Objectives

	Objective	Endpoint/Analysis
Exploratory	Determine mechanisms of resistance to FGFR inhibition at disease progression	Genomic profiling of pre-response tumor tissue and comparison with acquired resistance tumor specimen
Exploratory	Assess efficacy of BGJ398 (infigratinib) in relation to specific genetic aberrations in FGFR altered HNSCC (i.e. FGFR3-TACC3 translocation, FGFR1 high copy number/amplification, FGFR2 mutation, FGFR3 mutation)	Response Rate in subgroups of patients (as defined by certain genetic changes in FGFR1-3)
Exploratory	Efficacy by HPV status	Descriptive response rate in both HPV(+) and HPV(-) patients.

Overall, we hypothesize that:

- 1) *BGJ398 (infigratinib) will have clinical activity in FGFR altered HNSCC*
- 2) *BGJ398 (infigratinib) will demonstrate clinical activity in FGFR altered HNSCC*
- 3) *BGJ398 (infigratinib) will demonstrate clinical activity in all FGFR subgroups (i.e. FGFR1 high copy number/amplification, FGFR2 mutation, FGFR3 mutation, FGFR3 translocation)*
- 4) *Re-biopsy of patients who demonstrate initial response, followed by subsequent disease progression, will elucidate mechanisms of resistance to FGFR inhibition*

4 Investigational plan

Definitions

[figure not shown]
Cycle	A 4-week period of treatment with study medication BGJ398 (infigratinib)
End of treatment (EOT) visit	Clinic visit/assessment within 14 days of permanent termination of trial drug intake
End of post treatment follow-up	Clinic visit/assessment at Day 28 ± 8 days after the EOT visit

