22. Study medication cannot be administered through G-tube, unless additional information from the manufacturer becomes available in the future.

23. Women of child-bearing potential, defined as all women physiologically capable of becoming pregnant, unless they are using highly effective methods of contraception during dosing and for 3 months following the discontinuation of study treatment must be used by both sexes (=female patients and their male partners). Highly effective contraception methods include:
- Total abstinence (when this is in line with the preferred and usual lifestyle of the subject. Periodic abstinence (e.g., calendar, ovulation, symptothermal, post-ovulation methods) and withdrawal are not acceptable methods of contraception)
 - Female sterilization (have had surgical bilateral oophorectomy with or without hysterectomy) or tubal ligation at least six weeks before taking study treatment. In case of oophorectomy alone, only when the reproductive status of the woman has been confirmed by follow up hormone level assessment
 - Male sterilization (at least 6 months prior to screening). For female subjects on the study the vasectomized male partner should be the sole partner for that subject.
 - Combination of the following (a+b or a+c, or b+c):
 - a. Use of oral, injected or implanted hormonal methods of contraception or other forms of hormonal contraception that have comparable efficacy (failure rate <1%), for example hormone vaginal ring or transdermal hormone contraception
 - b. Placement of an intrauterine device (IUD) or intrauterine system (IUS)
 - c. Barrier methods of contraception: Condom or Occlusive cap (diaphragm or cervical/vault caps) with spermicidal foam/gel/film/cream/vaginal suppository

Note: Oral contraceptives (OC), injected or implanted hormonal methods are not allowed as the sole method of contraception because BGJ398 (infigratinib) has not been characterized with respect to the potential to interfere with PK and/or the effectiveness of OCs.

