Post-menopausal women are allowed to participate in this study. Women are considered post-menopausal and not of child bearing potential if they have had 12 months of natural (spontaneous) amenorrhea with an appropriate clinical profile (e.g. age appropriate, history of vasomotor symptoms) or have had surgical bilateral oophorectomy (with or without hysterectomy) or tubal ligation at least six weeks ago. In the case of oophorectomy alone, only when the reproductive status of the woman has been confirmed by follow up hormone level assessment is she considered not of child bearing potential.

24. Sexually active males unless they use a condom during intercourse while taking drug and for 3 months after the last dose of the study drug and should not father a child in this period. A condom is required to be used also by vasectomized men in order to prevent delivery of the drug via seminal fluid.

6 Treatment

The investigational drug will be BGJ398 (infigratinib) as an oral formulation.

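### The pregnancy reporting rule in section 10.5 lapses about 6 to 13 weeks before the protocol's own 3-month contraception period ends, so reporting in that gap is not expressly required

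*Combined protocol and SAP*

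**What the plan says.** Section 10.5 sets the rule: "Any pregnancy that occurs during study participation should be reported by the site". It adds that "each pregnancy must also be reported to Novartis within 24 hours of learning of its occurrence", and on outcome: "The pregnancy should be followed up to determine outcome, including spontaneous or voluntary termination, details of birth". No window after the last dose is given, and partners of male patients are not mentioned.

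The glossary defines the end of participation as "Point/time at which the patient came in for a final evaluation visit or when study treatment was discontinued whichever is later". Section 3.2 adds: "Trial termination is synonymous with off study / end of treatment". The definitions at the start of section 4 place the end-of-treatment (EOT) visit within 14 days of stopping the drug, and the last post-treatment visit as "Clinic visit/assessment at Day 28 ± 8 days after the EOT visit".

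Section 5.2 sets the contraception period. Criterion 23 applies to women of child-bearing potential and their partners "during dosing and for 3 months following the discontinuation of study treatment". Criterion 24 requires sexually active men to use a condom while on drug and "for 3 months after the last dose of the study drug and should not father a child in this period".

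**The concern.** Criteria 23 and 24 treat the 3 months after the last dose as a time when conception should be avoided. Section 10.5 is the only visible place that makes pregnancy itself reportable, and it is tied to participation, which ends earlier. A site that applies 10.5 as written need not report a pregnancy conceived after participation ends but inside the 3 months, and need not follow it to outcome.

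What is at stake is the information that 10.5 exists to collect: how the pregnancy ended, birth defects, and maternal or newborn complications. If that information is not gathered at the time, it may be hard to recover. In a multicenter study, an end of participation that is not tied to a named visit also invites sites to apply the rule differently. Criterion 24 restricts fathering a child, yet the visible text does not say whether a partner's pregnancy is to be reported.

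**Working it through.** The plan states no figure for this gap, so there is none to reproduce. The check counts days from the last dose (day 0).

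**Inputs**
- EOT visit: within 14 days of stopping, so day 0 to 14 (section 4 definitions).
- Post-treatment visit: EOT + 28 ± 8 days (section 4 definitions).
- Contraception period: 3 months after the last dose (criteria 23 and 24). Assumption: 91 days, with 84 (12 weeks) to 92 as the range.

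**End of participation under the glossary**
- If the EOT visit is the final evaluation: day 0 to 14.
- If the post-treatment visit is the final evaluation: earliest 0 + 28 − 8 = day 20; latest 14 + 28 + 8 = day 50.

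**Gap = end of contraception period − end of participation**

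| Reading of the final evaluation visit | Participation ends | Gap to day 91 | In weeks | Share of 91 days |
|---|---|---|---|---|
| EOT visit | day 0–14 | 77–91 days | 11.0–13.0 | 85–100% |
| Post-treatment visit | day 20–50 | 41–71 days | 5.9–10.1 | 45–78% |

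Sensitivity to the length of 3 months: at the latest end of participation (day 50) the gap is 84 − 50 = 34 days to 92 − 50 = 42 days. It stays positive on every reading. These are shares of days, not of pregnancies.

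**Do other provisions cover the gap?**
- Adverse events (6.4 and the visit schedule): followed for 30 days, which is 61 days short of day 91 if counted from the last dose.
- Pregnancy tests (visit schedule, note 7): the last scheduled test is at the EOT visit, day 14 at the latest.
- Serious adverse events (10.4.5): reportable until 4 weeks after participation stops. That is day 28–42 from an EOT-based end, or day 48–78 from the post-treatment visit, which is 13 to 63 days short. Later events remain reportable if a relationship to the drug is suspected. Section 10.3.2 lists a congenital anomaly as serious; pregnancy itself is not listed.
- Medical follow-up (10.6): at least 8 weeks after removal from study. If removal is at the last dose or the EOT visit, this ends at day 56–70, which is 21 to 35 days short. If removal is dated to the post-treatment visit, it ends at day 76–106 and may or may not reach day 91. The recommended 6 months (about day 182–196) would reach past it, but it is a recommendation and does not name pregnancy.
- Survival contacts (4.5 and 10.6): every 1 to 3 months, to 5 years. They run through the gap, but their stated purpose is survival.

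So several contacts span part or all of the gap, but none is stated to ask about or report pregnancy.

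**The case against.** A reader might infer that pregnancies conceived in the gap are never reported or followed, and that each is missed entirely. The documents do not support that. A drug-related birth defect, if suspected, stays reportable under 10.4.5 with no end date. Six months of medical follow-up is recommended, and survival contacts continue to 5 years, so a site may well learn of a pregnancy and report it.

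The end of participation is also partly a matter of interpretation. The glossary does not tie the final evaluation to a named visit, and 10.5 does not cite the glossary. The sentence on notifying the manufacturer has no time limit of its own. Section 13.2 speaks of keeping to the contraception requirement for the duration of the study, which could be read as placing the 3 months inside the study. A site could therefore read 10.5 broadly.

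Finally, section 13.2 makes the consent form part of the protocol. It is not in the public document and may deal with pregnancy notification or partners, as may the pregnancy form that 10.5 cites. The silence on partners in 10.5 is therefore not proof that the plan has no provision.

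All of this stands, and it limits the consequence that can be claimed. It does not remove the mismatch. The manufacturer sentence follows directly on the participation-limited one and most naturally refers to the same pregnancies. The late serious-event route covers a suspected drug-related event, not a normal birth or a voluntary termination. A broad reading is open to a site, but the text does not oblige it.

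**Conclusion.** The point holds as a mismatch between sections. The window in 10.5 closes between day 0 and day 50 after the last dose, 41 to 91 days (about 6 to 13 weeks) before the 3-month contraception period ends. In that gap, reporting a pregnancy and following its outcome are not expressly required and depend on site practice.

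This rests on the glossary meaning of participation, on the EOT or post-treatment visit being the final evaluation, and on 3 months being about 91 days; the gap persists from 84 to 92 days. It also rests on the visible text only.

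The practical size is small. The enrollment target is 20 patients, contraception is mandatory where relevant, and few events are expected; the number of patients able to conceive or father a child is not given. No endpoint, sample size or decision rule is affected. The case for acting is that the safety information could be important and the correction costs little: a cheap improvement.

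**What to change.** Reconcile 10.5 with criteria 23 and 24, using the 3-month figure the protocol already contains:

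1. Reword 10.5 along these lines: *A pregnancy conceived at any time from the start of study participation until 3 months after the last dose is to be reported within 24 hours of the site learning of it, and followed to outcome.* Nothing now reportable is lost.
2. State in 10.5 whether pregnancies in partners of male patients are included and, if so, that follow-up needs the partner's consent. If the consent form already covers this, a cross-reference is enough.
3. Add a question about pregnancy at the first survival contact at or after 3 months. Those contacts are already planned every 1 to 3 months.
4. Name the visit that ends participation, so that the other windows counted from it are unambiguous.

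The cost is a few sentences of protocol text, one question at an existing contact, possibly a partner consent form, and a few extra reports. Dosing, contraception requirements and clinical management are unchanged.
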